2.6.4 Handling of missing values not related to intercurrent event

For each of the CINDU cohort, the following will be considered as intermittent missing data, which are not related to intercurrent event:

- The provocation test is stopped due to any reason e.g. participant discomfort, technical issues the data will be considered as missing.
- The provocation test is not performed due to any reasons other than specified intercurrent events

Symptomatic dermographism

Handling of missing or incomplete results in the FricTest 4.0:

- The missing TFS=0 complete response status will be multiply imputed under the MAR assumption for all the groups.
- The missing itch NRS following the provocation test will be multiply imputed under the MAR assumption for all the groups.

Cold urticaria

Handling of missing or incomplete results in response to the TempTest®:

- The missing complete response status (a negative provocation test result for the lowest temperature (4°C) in TempTest®4.0) will be multiply imputed under the MAR assumption for all the groups.
- The missing itch NRS following the provocation test will be multiply imputed under the MAR assumption for all the groups.

Cholinergic urticaria

Handling of missing or incomplete results the following the pulse-controlled ergometry test:

- The missing itch NRS=0 complete response status will be multiply imputed under the MAR assumption for both treatment groups.

The missing PGA hive score=0 complete response status will be multiply imputed under the MAR assumption for both treatment groups.

2.6.5 Sensitivity analyses

No sensitivity analyses will be performed.

2.6.6 Supplementary analyses

No Supplementary analyses will be performed.

2.7 Safety analyses

The following applies to each of the three cohorts (i.e., symptomatic dermographism, cold urticaria, and cholinergic urticaria) separately, and in the overall CINDU population.

For all safety analyses (i.e. AEs, laboratory data, vital signs, and ECG), the SAF will be used. All data will be included in the analysis regardless of rescue medication use.

All listings and tables will be presented by treatment group.

Treatment groups for evaluation of treatment period

The summaries for evaluation of the treatment periods will allow for comparisons of treatment groups with placebo, before treatment switch is initiated. Therefore, the safety data for the Placebo-Ligelizumab 72mg/120mg q4w group will be provided in two separate periods.

As adverse event tables will be provided for the treatment period up to Week 12 separately, the Week 12 treatment period definition is the treatment period up to Week 12 dosing date (excluding the Week 12 dosing date). For the Placebo-Ligelizumab 72mg/120mg q4w group, if the first dosing date transitioning to ligelizumab happened earlier or later than the Week 12 dosing date (e.g. Week 4 or Week 8) due to a dosing error, the placebo treatment period will be cut-off by all the information prior to the first ligelizumab dosing date. The detailed description of the Week 12 cutoff date definition is provided in the statistical analysis plan appendix.

Treatment groups for evaluation of entire study

The summaries for evaluation of entire study will include all the information following the study design treatment groups. In addition, the following combined groups may be used for safety analysis.

Table 2-3 Treatment groups for safety analysis

	Ligelizumab 72mg q4w	Ligelizumab 120mg q4w	Placebo	Transitioned to Ligelizumab 72mg/120mg q4w
Treatment Period up to Week 12 visit	Yes ^a	Yes ^a	Yes ¹	No
Entire Study	Yes	Yes	No	Yes ²

¹ The information before the treatment switching is initiated will be included. It means only the safety information from the period when participants receive placebo will be included in the analysis.

² The information after the treatment transitioned is initiated will be included. It means only the safety information from the period when participants receive ligelizumab 72mg/120mg q4w will be included in the analysis.

^a The treatment groups will be included in the summary tables include information up to Week 12 visit.

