### Double-blinded treatment period

**Symptomatic dermographism and cold urticaria cohorts:** On Day 1, participants will be randomized equally into ligelizumab 120mg vs ligelizumab 72 mg vs placebo, with participants in the placebo arm being randomly re-allocated to ligelizumab 120 mg and ligelizumab 72 mg at week 12. Randomization will only be performed once at Day 1, in a 2:2:1:1 fashion into 4 arms: ligelizumab 120 mg, ligelizumab 72 mg, placebo to ligelizumab 120 mg and placebo to ligelizumab 72 mg.

During the treatment period, doses are administered at 6 visits; Week 0, Week 4, Week 8, Week 12, Week 16 and Week 20. No dose is administered at Week 1 (Day 8) visit. Participants randomized to the placebo arm will receive placebo for the first three treatment visits; Week 0, Week 4 and Week 8 and will then switch to ligelizumab 120 mg q4w or ligelizumab 72 mg q4w (1:1 ratio) for the remaining 3 treatment visits; Week 12, Week 16 and Week 20. Participants will continue to use their stable background therapy (H1-AH) at stable doses during the study.

**Cholinergic urticaria cohort:** On Day 1, participants will be randomized into a 1:1 fashion to ligelizumab 120 mg q4w vs. placebo. Participants of the placebo arm will be allocated to ligelizumab 120 mg at Week 12. Participants of the cholinergic urticaria cohort will not receive the ligelizumab 72 mg dose (see rationale in [Table 4.1](#)). During the treatment period, doses are administered at 6 visits; Week 0, Week 4, Week 8, Week 12, Week 16 and Week 20. No dose is administered at Week 1 (Day 8) visit. Participants randomized to the placebo arm will receive placebo for the first three treatment visits; Week 0, Week 4 and Week 8 and will then switch to

ligelizumab 120 mg q4w for the remaining 3 treatment visits; Week 12, Week 16 and Week 20. Participants will continue to use their stable background therapy (H1-AH) at stable doses during the study.

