#### **8.3.1.3 Pulse-controlled ergometry test**

To elicit symptoms of cholinergic urticaria in a clinical setting, pulse-controlled ergometry will be used. If a participant has risk factors for coronary artery disease, it is up to the discretion of the investigator to decide whether the patient needs cardiac clearance prior to undergoing the pulse controlled ergometry provocation test. In general, participants must be feeling well to perform this test. In this procedure, participants undergo pulse-controlled incremental ergometry for 30 min (stationary bicycle ride) increasing their pulse rate by 15 beats every 5 min to a final maximum increase of 90 beats per minute above the starting level at 30 min (Altrichter et al 2014). A pulse oximeter is fitted to the participant to monitor pulse rate. Only participants that are able to sweat should be included in the cholinergic urticaria cohort, hence, to detect sweating on day of randomization, starch-iodine powder or similar is applied to the lower back or other area that shows sweating. This sweat detection test must be performed on all provocation test days and is described in the provocation test manual for cholinergic urticaria.

The start time of sweating and the start time that hives appear are recorded on the eCRF. Time to appearance of hives correlates with disease activity; in other words, the sooner the hives appear, the more active the disease (Altrichter et al 2014). Observations are continued during a 10 min recovery period at the end of the 30 min of exercise.

Itchy hives are considered a positive response. Ten minutes after the end of the provocation test, the participant is asked to evaluate the severity of their itch, pain and burning using a 11 point numerical rating scale ranging from no symptom (scored 0) to worst possible symptom (scored 10). The investigator will also assess the severity of hives using the physician global assessment of severity of hives.

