1.1.2 Double-blinded treatment period

As a result of study termination, all subjects in the treatment phase were discontinued from treatment and moved into the follow-up phase. Only 3 subjects had completed Week 12 visit.

Below is a description of the treatment period as per protocol:

Symptomatic dermatographism and cold urticaria cohorts: On Day 1, participants were randomized equally into ligelizumab 120mg vs ligelizumab 72 mg vs placebo, with participants in the placebo arm being randomly re-allocated to ligelizumab 120 mg and ligelizumab 72 mg at week 12. Randomization will only be performed once at Day 1, in a 2:2:1:1 fashion into 4 arms: ligelizumab 120 mg, ligelizumab 72 mg, placebo to ligelizumab 120 mg and placebo to ligelizumab 72 mg.

During the treatment period, doses are administered at 6 visits: Week 0, Week 4, Week 8, Week 12, Week 16 and Week 20. Participants randomized to the placebo arm will receive placebo for the first three treatment visits; Week 0, Week 4 and Week 8 and will then switch to ligelizumab 120 mg q4w or ligelizumab 72 mg q4w (1:1 ratio) for the remaining 3 treatment visits; Week 12, Week 16 and Week 20. Participants will continue to use their stable background therapy (H1-AH) at stable doses during the study.

Cholinergic urticaria cohort: On Day 1, participants will be randomized into a 1:1 fashion to ligelizumab 120 mg q4w vs. placebo. Participants of the placebo arm will be allocated to ligelizumab 120 mg at Week 12. Participants of the cholinergic urticaria cohort will not receive the ligelizumab 72 mg dose. During the treatment period, doses are administered at 6 visits: Week 0, Week 4, Week 8, Week 12, Week 16 and Week 20. Participants randomized to the placebo arm will receive placebo for the first three treatment visits; Week 0, Week 4 and Week 8 and will then switch to ligelizumab 120 mg q4w for the remaining 3 treatment visits; Week 12, Week 16 and Week 20. Participants will continue to use their stable background therapy (H1-AH) at stable doses during the study.

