2.7.1 Adverse events (AEs)

Treatment emergent adverse events (TEAEs) are events which started on or after the first dose of study treatment and within 16 weeks after the last study treatment, or events present prior to the first dose of study treatment but increased in severity based on preferred term within 16 weeks after the last study treatment.

TEAEs will be summarized in each cohort separately by the actually received treatment group:

- The number and exposure-adjusted incidence of subjects having any TEAE by system organ class (SOC) and preferred term (PT): For the participants in the placebo arm, adverse events after switching to ligelizumab (on or after Week 12) will be summarized separately for the treatment phase. The summary of the TEAEs up to Week 12 will include all the TEAEs up to Week 12 for all the treatment groups, including the placebo only group. The summary of the TEAEs for the entire study will be provided for all the treatment groups listed in Table 2-3.
- The number and exposure-adjusted incidence of subjects having any TEAE by severity: if a subject reported more than one adverse event with the same preferred term, the adverse event with the greatest severity will be presented. If a subject reported more than one adverse event within the same primary system organ class, the subject will be counted only once with the greatest severity at the system organ class level, where applicable.
- The number and exposure-adjusted incidence of subjects having any related TEAEs.: if a subject reported more than one adverse event with the same preferred term, the adverse event with the greatest severity will be presented. If a subject reported more than one adverse event within the same primary system organ class, the subject will be counted only once with the greatest severity at the system organ class level, where applicable.
- The number exposure-adjusted incidence of subjects having any serious treatment emergent adverse events (TESAEs), related TESAEs. The following significant adverse event will be listed - TEAEs leading to discontinuation and dose interruption, and TEAE adverse events of special interest (AESIs). For AESIs with adjudication (anaphylaxis, malignancy, CCV), separate listings will be provided based on the adjudicated results.
- A listing will be provided for safety topics of immunogenicity, COVID-19 infection, Liver Toxicity.

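### SAP 2.7 extends the by-arm safety output to the overall CINDU population, against the by-cohort text elsewhere; a crude overall table would confound the 72 mg comparisons with disease subtype

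*SAP*

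**What the plan says.** The first sentence of SAP 2.7 reads: "The following applies to each of the three cohorts (i.e., symptomatic dermographism, cold urticaria, and cholinergic urticaria) separately, and in the overall CINDU population". The section then states "All listings and tables will be presented by treatment group" and, for the placebo-controlled period, "The summaries for evaluation of the treatment periods will allow for comparisons of treatment groups with placebo, before treatment switch is initiated". Table 2-3 gives the safety columns: one for 72 mg, one for 120 mg, one for placebo and one for participants who switched from placebo. It has no cohort restriction and no rule for stratifying or weighting by subtype.

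Other parts of the SAP point the other way. Section 2.2 says summary statistics are produced in each cohort on its own. Section 2.7.1 says "TEAEs will be summarized in each cohort separately by the actually received treatment group". Sections 2.7.1.2 (events of special interest), 2.7.3 (laboratory) and 2.7.4.1 (ECG) give the same instruction. Table 2-2 carries a footnote that the 72 mg columns do not apply to the cholinergic cohort; Table 2-3 carries no such note. Protocol 12.5.2 applies the safety analyses to all three subtypes and mentions no pooled population.

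On allocation, the Protocol (3.1, double-blinded treatment period) says "Participants of the cholinergic urticaria cohort will not receive the ligelizumab 72 mg dose". For dermographism and cold urticaria, SAP 1.1.2 says "Randomization will only be performed once at Day 1, in a 2:2:1:1 fashion into 4 arms". That is 1:1:1 for 120 mg, 72 mg and placebo up to Week 12. The cholinergic cohort is randomized 1:1 to 120 mg or placebo.

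**The concern.** Randomization took place within cohorts, and one cohort has no 72 mg arm. If the three cohorts are added together and tabulated by arm, the 72 mg column and the other two columns describe different mixes of disease. Any difference between subtypes in background adverse events would then appear as an effect of the 72 mg dose or as a dose trend, even if every within-cohort comparison were null. A real excess on 72 mg could be hidden in the same way.

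The protocol gives one reason why background rates might differ. In the cholinergic cohort "participants undergo pulse-controlled incremental ergometry for 30 min", whereas the other two cohorts have a local skin test. That is a possible mechanism, not evidence of a difference.

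The stake is the reading of an overall safety table. No efficacy result is involved, and no formal safety test is planned.

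**Working it through.** **Planned numbers (Protocol 3.1 and 5; SAP 1.1.2).** Dermographism 168/3 = 56 per arm; cold urticaria 102/3 = 34 per arm; cholinergic 158/2 = 79 per arm. Total 168 + 102 + 158 = 428, as stated.

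**Make-up of the pooled columns up to Week 12.**

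| Column | Dermographism | Cold | Cholinergic | Total | Cholinergic share |
|---|---|---|---|---|---|
| 72 mg | 56 | 34 | 0 | 90 | 0% |
| 120 mg | 56 | 34 | 79 | 169 | 79/169 = 46.7% |
| Placebo | 56 | 34 | 79 | 169 | 79/169 = 46.7% |

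**Bias with no drug effect in any cohort.** Let c be the event proportion in cholinergic participants and o the proportion in the other two cohorts.

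- 72 mg column: o
- Placebo and 120 mg columns: (90 × o + 79 × c)/169
- Crude difference, 72 mg minus either: −(79/169) × (c − o) = −0.467 × (c − o)

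**Size.** The documents give no event rates by subtype, so these values are assumptions.

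| Others (o) | Cholinergic (c) | 72 mg | Placebo and 120 mg | 72 mg minus placebo |
|---|---|---|---|---|
| 20% | 20% | 20.0% | 20.0% | 0 |
| 20% | 30% | 20.0% | 24.7% | −4.7 points |
| 10% | 30% | 10.0% | 19.3% | −9.3 points |
| 30% | 20% | 30.0% | 25.3% | +4.7 points |
| 30% | 10% | 30.0% | 20.7% | +9.3 points |

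The 120 mg minus placebo difference is 0 in every row, because those two columns have the same planned mix. In the 20%/30% row, a true 5-point excess on 72 mg would appear as 25.0 − 24.7 = +0.3 points.

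**After the switch.** If the switched group is split by dose, placebo-to-72 mg has 28 + 17 = 45 people, none cholinergic. Placebo-to-120 mg has 28 + 17 + 79 = 124, of whom 79/124 = 63.7% are cholinergic.

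**At actual enrolment.** SAP 1.1 gives 39 enrolled, without a cohort split. Suppose k of them are cholinergic and that all were randomized in the planned ratios. The cholinergic share of pooled placebo is then (k/2)/[(39 − k)/3 + k/2]. For k = 5 this is 2.5/13.8 = 18%; for k = 20 it is 10/16.3 = 61%. The 72 mg share is 0% throughout.

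**With the pool restricted.** Keeping only the two cohorts that have all three arms gives 90/90/90, each 62.2% dermographism (56/90) and 37.8% cold urticaria (34/90). The spurious difference is then 0 in every row above.

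**The case against.** The strongest reply is that no pooled adverse event table is actually specified. The overall population appears in one introductory phrase, while the subsections that define the outputs say cohort by cohort. Table 2-3 is introduced permissively, as combined groups that may be used. Deaths, laboratory, ECG and vital signs are planned mainly as listings, and pooling does not confound a listing of individual data. The SAP was also written after termination: 39 were enrolled, 3 had completed Week 12, and it rules out statistical analyses on any dataset. A 72 mg arm could hold at most 39/3 = 13 people, so a 9.3-point shift is about 0.093 × 13 = 1.2 participants. Finally, the planned metric is a count with an exposure-adjusted rate, not a crude percentage.

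Most of this stands, and it limits the point. A reader might infer that the SAP commits to a misleading pooled table, or that 72 mg would look about 9 points safer. The documents support neither: the pool is announced but not laid out, and the 9.3 points rest on an assumed 20-point gap whose direction could equally be reversed. Nor do they show that the ergometry test produces more adverse events than the skin tests.

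The reply does not remove the conflict. The opening rule governs the whole section, and nothing in it prevents a crude pool. Exposure-adjusted rates with exact Poisson intervals are still described in SAP 2.7.1.1. Exposure adjustment does not correct for subtype mix; it only changes the weights from head counts to exposure time.

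**Conclusion.** SAP 2.7 conflicts with SAP 2.2, 2.7.1, 2.7.1.2, 2.7.3 and 2.7.4.1 on whether safety is shown for the overall population. If an overall by-arm table is produced as 2.7 allows, its crude comparisons of 72 mg with placebo and with 120 mg are confounded by subtype.

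The imbalance is certain by design: 0% against 46.7% cholinergic at planned numbers. The resulting bias is not known. It depends on subtype event rates that the documents do not give, and it is zero if those rates are equal.

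Two wider inferences should be resisted. Pooled 120 mg versus placebo is not affected at planned numbers. The cohort-level tables remain valid and would let a reader see whether an apparent 72 mg difference is real. With descriptive output and a terminated trial, this is a small correction worth making, not a threat to the trial's conclusions.

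**What to change.** Choose one of two edits to SAP 2.7.

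1. If no pooled output is intended, keep only the first word of "separately, and in the overall CINDU population" in the opening sentence, so that it matches the by-cohort text.
2. If an overall table is wanted, state that 72 mg is shown only against placebo and 120 mg participants from the dermographism and cold urticaria cohorts, or that rates are stratified by cohort. Use the three-cohort pool only for 120 mg versus placebo.

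In either case, add to Table 2-3 the Table 2-2 footnote that 72 mg does not apply to the cholinergic cohort.

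The first option costs one deletion. The second costs about one sentence and one extra table or cohort filter. Neither needs new data or adds burden for participants.

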2.7.1 Adverse events (AEs)

Treatment emergent adverse events (TEAEs) are events which started on or after the first dose of study treatment and within 16 weeks after the last study treatment, or events present prior to the first dose of study treatment but increased in severity based on preferred term within 16 weeks after the last study treatment.

TEAEs will be summarized in each cohort separately by the actually received treatment group:

- The number and exposure-adjusted incidence of subjects having any TEAE by system organ class (SOC) and preferred term (PT): For the participants in the placebo arm, adverse events after switching to ligelizumab (on or after Week 12) will be summarized separately for the treatment phase. The summary of the TEAEs up to Week 12 will include all the TEAEs up to Week 12 for all the treatment groups, including the placebo only group. The summary of the TEAEs for the entire study will be provided for all the treatment groups listed in Table 2-3.
- The number and exposure-adjusted incidence of subjects having any TEAE by severity: if a subject reported more than one adverse event with the same preferred term, the adverse event with the greatest severity will be presented. If a subject reported more than one adverse event within the same primary system organ class, the subject will be counted only once with the greatest severity at the system organ class level, where applicable.
- The number and exposure-adjusted incidence of subjects having any related TEAEs.: if a subject reported more than one adverse event with the same preferred term, the adverse event with the greatest severity will be presented. If a subject reported more than one adverse event within the same primary system organ class, the subject will be counted only once with the greatest severity at the system organ class level, where applicable.
- The number exposure-adjusted incidence of subjects having any serious treatment emergent adverse events (TESAEs), related TESAEs. The following significant adverse event will be listed - TEAEs leading to discontinuation and dose interruption, and TEAE adverse events of special interest (AESIs). For AESIs with adjudication (anaphylaxis, malignancy, CCV), separate listings will be provided based on the adjudicated results.
- A listing will be provided for safety topics of immunogenicity, COVID-19 infection, Liver Toxicity.

For the legal requirements of ClinicalTrials.gov and EudraCT, two required tables with treatment emergent adverse events which are not serious adverse events with an incidence greater than 5% and with treatment emergent serious adverse events and SAEs suspected to be related to study treatment, will be provided by system organ class and preferred term on the safety set population. These tables will not be included in the CSR.

If for the same participant, several consecutive TEAEs (irrespective of study treatment causality, seriousness and severity) occurred with the same SOC and PT:

- a single occurrence will be counted if there is ≤ 1 day gap between the end date of the preceding TEAE and the start date of the consecutive TEAE.
- more than one occurrence will be counted if there is > 1 day gap between the end date of the preceding TEAE and the start date of the consecutive TEAE.

For occurrence, the presence of at least one TESAE / TESAE suspected to be related to study treatment / non TESAE has to be checked in a block e.g., among TEAE's in a ≤ 1 day gap block. If at least one SAE is occurring, then one occurrence is calculated for that TESAE.

The number of deaths resulting from TESAEs suspected to be related to study treatment and TESAEs irrespective of study treatment relationship will be provided by SOC and PT.

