## **Adverse events**

All information obtained on AEs will be displayed by treatment group (or sequence) and participant.

Treatment emergent AEs will be summarized by actually received treatment.

Treatment emergent AEs (TEAE) are defined as:

- Events started after the first dose of study treatment (ligelizumab) in this study and within 16 weeks of last dose of study treatment
- Events present prior to the first dose of study treatment (ligelizumab) in this study but:
  1. increased in severity based on preferred term (e.g. worsening of headache),
  2. same PT but increased severity (e.g. from mild to moderate),
  3. same PT but increase in seriousness (from non-serious AE to SAE; if already a SAE from medical significant to LT/fatal)and within 16 weeks after the last dose of the study treatment.

The number (and percentage) of participants with treatment emergent AEs will be summarized in the following ways:

- by treatment, primary system organ class and preferred term.
- by treatment, primary system organ class, preferred term and maximum severity.
- by treatment, Standardized MedDRA Query (SMQ) and preferred term.

Separate summaries will be provided for study medication related AEs, death, SAEs, other significant adverse events leading to treatment discontinuation.

The number (and proportion) of participants with treatment emergent AEs of special interest (AESI) will be summarized by treatment.

The number (and proportion) of participants with treatment emergent AEs related to other safety topics such as events related to “liver toxicity” will be summarized by treatment.

A participant with multiple AEs within a primary system organ class is only counted once towards the total of the primary system organ class.

For the placebo-ligelizumab treatment group, treatment-emergent AEs will be counted separately for the placebo treatment and ligelizumab treatment.

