2.7.2 Deaths

Death will be reported as part of TESAE with a fatal outcome and will be listed in separate listings.

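### SAP 2.7.1 counts a pre-dose event as treatment-emergent only if severity increases, while Protocol 12.5.2 also counts an increase in seriousness, so some TESAEs can be missed

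*SAP*

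**What the plan says.** Protocol 12.5.2 (Adverse events) lists separate grounds on which an event present before the first dose becomes treatment-emergent. One is severity: "same PT but increased severity (e.g. from mild to moderate"). Another is seriousness: "same PT but increase in seriousness (from non-serious AE to SAE; if already a SAE from medical significant to LT/fatal"). Both apply within 16 weeks after the last dose.

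SAP 2.7.1 has a single ground for such events: "events present prior to the first dose of study treatment but increased in severity based on preferred term". The time limit is again 16 weeks from the last dose. Seriousness is not mentioned.

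Several SAP outputs depend on the treatment-emergent flag:
- The SAE summary in 2.7.1 is "The number exposure-adjusted incidence of subjects having any serious treatment emergent adverse events (TESAEs), related TESAEs".
- One of the registry tables in 2.7.1 is specified "with treatment emergent serious adverse events and SAEs suspected to be related to study treatment".
- For deaths, 2.7.2 says: "Death will be reported as part of TESAE with a fatal outcome and will be listed in separate listings".

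**The concern.** Severity and seriousness are different attributes. Protocol 10.1.1 has the site record the CTC grade and the SAE status as separate items, and Protocol 10.1.2 defines an SAE by outcome or medical significance, not by grade. A rule that looks only at grade can therefore miss an event whose seriousness changes on treatment.

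This matters more than usual because the trial was terminated. SAP Sections 1 and 4 cancel the formal tests and the efficacy summary tables, so the TEAE and TESAE summaries are among the main outputs left. Termination gives no reason to narrow the TEAE definition, and SAP Section 1 says its sections follow the protocol, with termination language added.

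**Working it through.** The plan gives no figure to reproduce. The check is a comparison of texts, followed by a direction-of-effect argument.

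**Step 1: classify the cases.** Take an AE that starts after consent and before the first dose, keeps the same preferred term, and changes within 16 weeks after the last dose.

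| What changes | Protocol 12.5.2 | SAP 2.7.1 |
|---|---|---|
| CTC grade rises, stays non-serious | TEAE | TEAE |
| CTC grade rises, becomes an SAE | TESAE | TESAE |
| CTC grade unchanged, non-serious to SAE | TESAE | not a TEAE |
| CTC grade unchanged, medically significant SAE becomes life-threatening or fatal | TESAE | not a TEAE |
| Site opens a new record with a post-dose start | TESAE | TESAE |

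The definitions part in rows 3 and 4. Row 4 should be almost empty, because a move to life-threatening or fatal would normally raise the CTC grade as well. Row 3 is the real exposure.

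**Step 2: look for a rule elsewhere that restores the criterion.** There is none in the rest of SAP 2.7, in the Week 12 cut-off rules (SAP 5.2) or in the AE date rules (SAP 5.3.2). SAP 5.4 on AE coding and grading is marked not applicable. The visible items of SAP Section 4 do not mention the TEAE definition.

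**Step 3: who is at risk.** AEs are collected from informed consent (Protocol 10.1.1) and screening lasts up to 28 days (Protocol 3.1 and Table 8-1). Conditions already present at consent go to medical history (Protocol 10.1.1). The pool is therefore essentially AEs that start between consent and first dose.

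**Step 4: direction of the effect.** A TESAE must first be a TEAE, so a narrower TEAE definition can remove a TESAE but cannot add one.

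For the rates, SAP 2.7.1.1 uses EAIR = n / Σt. Each t is the shortest of time to first event, treatment duration plus 16 weeks, and time to the end of the analysis period. Assume time to event runs to the change in seriousness, and let d ≥ 0 be the exposure time added when the event is not counted.
- If it was the participant's only qualifying event, the rate goes from n / Σt to (n − 1) / (Σt + d), which is lower.
- If the participant has another qualifying event, n is unchanged and the rate becomes n / (Σt + d), which is lower or the same.

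In neither case does the rate rise.

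**Step 5: number of events.** Neither document gives a count or rate of AEs that turn serious at an unchanged grade, so no number can be derived.

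**The case against.** The strongest case on the other side is that the affected set is close to empty and that the SAP may not have departed from its own source.

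- **Protocol version.** The SAP says it is based on protocol version 0.0. The supplied protocol appears to be later: it has eight treatment-period visits including Week 1 (Protocol 3.1), against seven in SAP 1.1, and it names visit 105 among the remote visits where the SAP does not. A reader might infer that the sponsor deliberately removed the criterion. The documents do not support that, because version 0.0 cannot be seen. The mismatch with the supplied protocol stands.
- **Section 4 silence.** Two items in that list are redacted, so only the visible part can be called silent. This stands as a limit.
- **SAE definition.** Protocol 10.1.2 requires appearance or worsening of a condition, and it excludes routine, pre-planned and social admissions without deterioration. This removes many hospitalizations at an unchanged grade. It leaves unplanned admissions, and events judged medically significant, where the condition worsens within the same grade.
- **Recording practice.** Protocol 10.1.3 asks for a separate report when an SAE occurs at a different time interval from one already reported. A new post-dose record would be counted. The same section, however, treats progression of an initial SAE as follow-up to the original episode, and Protocol 10.1.1 follows an AE until it resolves. Neither document fixes the eCRF start date for a non-serious AE that becomes serious, so this point is open.
- **Reach.** A reader might infer that every SAE, registry and death output is understated. That goes too far. The registry wording names related SAEs without clearly repeating the treatment-emergent condition, so it may still catch those. A fatal change would normally qualify through its grade.

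**Conclusion.** The two definitions disagree, and following the SAP as written can leave out a TESAE that the supplied protocol defines. The error runs one way: TESAE counts and exposure-adjusted rates can be too low, never too high.

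The size is unknown and probably small. It is confined in practice to AEs starting between consent and first dose that become SAEs at an unchanged CTC grade and are kept on the original record. The effect on the death outputs, and on related SAEs in the registry tables, is weak.

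It may be tempting to express one missed participant as a percentage of a planned arm (34 to 79 participants) or of the 39 enrolled. That would not be an effect size. The planned arms were never filled, the 39 pool all cohorts and treatments, and the tables report exposure-adjusted rates by cohort and treatment.

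The conclusion rests on the supplied protocol being the governing one and on no redacted SAP text restoring the criterion. The point is worth correcting because it concerns a protocol-defined safety rule in tables that survive termination and because the correction is cheap. It is not evidence that any SAE has been missed.

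**What to change.** In SAP 2.7.1, extend the limb on events present before the first dose so that, inside the existing 16-week window, it also covers an increase in seriousness under the same preferred term: non-serious to SAE, or a medically significant SAE becoming life-threatening or fatal. This criterion then agrees with Protocol 12.5.2.

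If the narrower rule is intended, declare and justify it in SAP Section 4 instead.

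The cost is one clause and one check of the TEAE derivation. The check should confirm how the database dates an AE that changes from non-serious to serious, since that decides whether any event is affected. No new data are needed.
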